**Investigator Interests:**

Does the principal investigator, or do any research personnel who are responsible for the design, conduct or reporting of this project or any of their family members (spouse or dependent child) have an incentive or interest, financial or otherwise, that may affect the protection of the human subjects involved in this project, the scientific objectivity of the research or its integrity? Note: The Principal Investigator (Project Director), upon consideration of the individual's role and degree of independence in carrying out the work, will determine who is responsible for the design, conduct, or reporting of the research.

See Disclosures and Management of Personal Interests in Human Research

<http://www.yale.edu/hrpp/policies/index.html#COI>

Yes       No

Do you or does anyone on the research team who is determined by you to be responsible for the design, conduct or reporting of this research have any patent (sole right to make, use or sell an invention) or copyright (exclusive rights to an original work) interests related to this research protocol?

Yes       No

If yes to either question above, list names of the investigator or responsible person:

*The Yale University Principal Investigator, all Yale University co-investigators, and all Yale University individuals who are responsible for the design, conduct or reporting of research must have a current financial disclosure form on file with the University's Conflict of Interest Office. Yale New Haven Hospital personnel who are listed as co-investigators on a protocol with a Yale University Principal Investigator must also have a current financial disclosure form on file with the University's Conflict of Interest Office. If this has not been done, the individual(s) should follow this link to the COI Office Website to complete the form: <http://www.yale.edu/coi/>*

**NOTE:** The requirement for maintaining a current disclosure form on file with the University's Conflict of Interest Office extends primarily to Yale University and Yale-New Haven Hospital personnel. **Whether or not they are required to maintain a disclosure form with the University's Conflict of Interest Office, all investigators and individuals deemed otherwise responsible by the PI who are listed on the protocol are required to disclose to the PI any interests that are specific to this protocol.**

SECTION II: GENERAL INFORMATION
--

1. **Performing Organizations:** Identify the hospital, in-patient or outpatient facility, school or other agency that will serve as the location of the research. Choose all that apply:

**c. Additional Required Documents (check all that apply):**

 *YCCI-Scientific and Safety Committee (YCCI-SSC)	 N/A
 *Pediatric Protocol Review Committee (PPRC)	Approval Date:
 *YCC Protocol Review Committee (YRC-PRC)	Approval Date:
 *Dept. of Veterans Affairs, West Haven VA HSS	Approval Date:
 *Radioactive Drug Research Committee (RDRC)	Approval Date:
 YNHH-Radiation Safety Committee (YNHH-RSC)	Approval Date:
 Magnetic Resonance Research Center PRC (MRRC-PRC)	Approval Date:
 YSM/YNHH Cancer Data Repository (CaDR)	Approval Date:
 Dept. of Lab Medicine request for services or specimens form	
 Imaging on YNHH Diagnostic Radiology equipment request form (YDRCTO request) found at http://radiology.yale.edu/research/ClinTrials.aspx	

*\*Approval from these committees is required before final HIC approval is granted. See instructions for documents required for initial submission and approval of the protocol. Allow sufficient time for these requests. Check with the oversight body for their time requirements.*

2. **Probable Duration of Project:** State the expected duration of the project, including all follow-up and data analysis activities. 4 Years

3. **Research Type/Phase: (Check all that apply)**

a. **Study Type**

Single Center Study  
 Multi-Center Study

Does the Yale PI serve as the PI of the multi-site study? Yes

No

Coordinating Center/Data Management  
 Other:

b. **Study Phase**  N/A  
 Pilot  Phase I  Phase II  Phase III  Phase IV  
 Other (Specify)

4. **Area of Research: (Check all that apply)** Note that these are overlapping definitions and more than one category may apply to your research protocol. Definitions for the following can be found in the instructions section 4c:

 Clinical Research: Patient-Oriented	 Clinical Research: Outcomes and Health Services
 Clinical Research: Epidemiologic and Behavioral	 Interdisciplinary Research
 Translational Research #1 ("Bench-to-Bedside")	 Community-Based Research
 Translational Research #2 ("Bedside-to-Community")	

5. Is this study a clinical trial? Yes  No

*NOTE the current ICMJE (International Committee of Medical Journal Editors) definition of a clinical trial: "any research study that prospectively assigns human participants or groups of humans to one or more health-related interventions to evaluate the effects on health outcomes." Health-related interventions include any intervention used to modify a biomedical or health-related outcome (for example, drugs, surgical procedures, devices, behavioral treatments, dietary interventions, and process-of-care changes). Health outcomes include any biomedical or health-related measures obtained in patients or participants, including pharmacokinetic measures and adverse events"*

If yes, where is it registered?

Clinical Trials.gov registry   
 Other (Specify)

Registration of clinical trials at their initiation is required by the FDA, NIH and by the ICMJE.

*If this study is registered on clinicaltrials.gov, there is new language in the consent form and compound authorization that should be used.*

For more information on registering clinical trials, including whether your trial must be registered, see the YCCI webpage,  
<http://ycci.yale.edu/researchers/ors/registerstudy.aspx> or contact YCCI at [contact])

6. Does the Clinical Trials Agreement (CTA) require compliance with ICH GCP (E6)?  
 Yes  No

7. Will this study have a billable service? A Billable Service is defined as a service or procedure that will be ordered, performed or result in charging in EPIC for individuals who are enrolled in a clinical research study, regardless if the charge is intended to be paid by the subject/their insurance or the research study.

Yes  No 

If you answered "yes", this study will need to be set up in OnCore Support

<http://medicine.yale.edu/ymg/systems/ppm/index.aspx>

8..Are there any procedures involved in this protocol that will be performed at YNHH or one of its affiliated entities? Yes  No  *If Yes, please answer questions a through c and note instructions below. If No, proceed to Section III.*

- a. Does your YNHH privilege delineation currently include the **specific procedure** that you will perform?
- b. Will you be using any new equipment or equipment that you have not used in the past for this procedure?
- c. Will a novel approach using existing equipment be applied?

If you answered "no" to question 7a, or "yes" to question 7b or c, please contact the YNHH Department of Physician Services ([name]) for prior approval before commencing with your research protocol.

### SECTION III: FUNDING, RESEARCH TEAM AND TRAINING

1. **Funding Source:** Indicate all of the funding source(s) for this study. Check all boxes that apply.

Provide information regarding the external funding source. This information should include identification of the agency/sponsor, the funding mechanism (grant or contract), and whether the award is pending or has been awarded. Provide the M/C# and Agency name (if grant-funded). If the funding source associated with a protocol is "pending" at the time of the protocol submission to the HIC (as is the case for most NIH submissions), the PI should note "Pending" in the appropriate section of the protocol application, provide the M/C# and Agency name (if grant-funded) and further note that University (departmental) funds support the research (until such time that an award is made).

PI	Title of Grant	Name of Funding Source	Funding	Funding Mechanism
[name]	Ketamine Infusion for Social Anxiety Disorder	Patterson Trust Award	 Federal  State  Non Profit  Industry  Other For Profit  Other	 Grant-M#  Contract#  Contract Pending  Investigator/Department Initiated  Sponsor Initiated  Other, Specify:

		 Federal  State  Non Profit  Industry  Other For Profit  Other	 Grant-M#  Contract#  Contract Pending  Investigator/Department Initiated  Sponsor Initiated  Other, Specify:
		 Federal  State  Non Profit  Industry  Other For Profit  Other	 Grant-M#  Contract#  Contract Pending  Investigator/Department Initiated  Sponsor Initiated  Other, Specify:

IRB Review fees are charged for projects funded by Industry or Other For-Profit Sponsors. Provide the Name and Address of the Sponsor Representative to whom the invoice should be sent. ***Note: the PI's home department will be billed if this information is not provided.***

### SECTION V: RESEARCH PLAN

#### 1. Statement of Purpose: State the scientific aim(s) of the study, or the hypotheses to be tested.

***To determine the short-term efficacy of ketamine compared to placebo in the treatment of severe social anxiety disorder (SAD).*** We will conduct a crossover trial in which 18 patients with severe SAD will be given a single infusion of ketamine or saline (placebo) and their SAD symptoms will be followed over a two week period. We will require 4 weeks between infusion doses in order to minimize carryover effects. Our primary outcome will be average improvement during the first 3 days following infusion on the Visual Analog Scale (VAS) of Anxiety States.

#### 2. Background: Describe the background information that led to the plan for this project. Provide references to support the expectation of obtaining useful scientific data.

- Social Anxiety Disorder is common and causes significant impairment.
- First-line treatments for Social Anxiety Disorder are only partially effective. Many SAD patients experience little or inadequate symptom relief with available treatments.
- Ketamine is a potent NMDA receptor antagonist. Ketamine represents an agent with a potentially novel mechanism of action for the treatment of anxiety disorders.
- Ketamine has demonstrated efficacy in the treatment of psychiatric disorders closely related to Social Anxiety Disorder including Major Depression, Bipolar Depression and possibly Obsessive-Compulsive Disorder.

Social anxiety disorder (SAD) affects approximately 12.1% of all Americans and is defined as a “marked and persistent fear of one or more social situations,” causing impairment and distress(Kessler, Peters et al. 2005). SAD typically impairs academic achievement, work productivity, social relationships, and results in a significantly poorer quality of life (Lipsitz and Schneier 2000). SAD is associated with subsequent development of depression, alcoholism, and cardiovascular disease (Kessler 2003, Kessler, Peters et al. 2005).

Roughly one-third to one-half of patients with generalized SAD do not experience significant clinical benefit from current evidence-based treatment for SAD such as pharmacotherapy with selective serotonin reuptake inhibitors (SSRI) or venlafaxine and cognitive behavioral therapy (CBT) (Blomhoff, Spetalen et al. 2001, Davidson 2004, Baldwin, Anderson et al. 2005, Baldwin and Nair 2005). Failure of anxiety relief in patients with SAD is a source of substantial morbidity, distress, and decreases in quality of life. Novel pharmacological treatments are needed to improve patient outcomes with SAD.

Converging lines of evidence from neuroimaging and pharmacological studies support the importance of glutamate abnormalities in the pathogenesis of SAD. In a Magnetic Resonance Spectroscopy (MRS) study, an elevated glutamate to creatinine ratio was found in the anterior cingulate cortex of SAD patients when compared to healthy controls (Phan, Fitzgerald et al. 2005). Elevated thalamic glutamine levels have been demonstrated in patients with SAD (Pollack, Jensen et al. 2008). Pre-clinical rodent studies have also established a strong link between glutamate regulation and anxiety (Linden 2002, Walker and Davis 2002, Bergink, van Megen et al. 2004, Johnson, Inderbitzen-Nolan et al. 2005).

Ketamine is a potent antagonist of the N-methyl-D-aspartate (NMDA) receptor, a major type of glutamate receptor in the brain. Ketamine is routinely used for anesthetic induction because of its dissociative properties. However in research studies, ketamine is effective treatment in reducing symptoms in depressive and possibly anxiety disorders. In multiple controlled clinical studies, ketamine has produced a rapid antidepressant effect in unipolar and bipolar depression(Berman, Cappiello et al. 2000, Zarate, Singh et al. 2006, Maeng and Zarate 2007, Murrough, Perez et al. 2011, Valentine, Mason et al. 2011). Ketamine’s anti-depressant effects peak 1-3 days following infusion. Ketamine’s antidepressant effect is observed long after ketamine has been metabolized and excreted by the body and after ketamine’s sedative and dissociative effects have dissipated (Figure 1-3).

Figure 1: RM Berman et al (2000)

[figure not shown]

Figure 2: CA Zarate et al (2006)

[figure not shown]
[figure not shown]

Figure 3: GW Valentine et al (2011)

The results of several clinical studies suggest that ketamine may also have significant anxiolytic effects. Patients with major depressive disorder given a single ketamine infusion have shown strong and significant reductions in comorbid anxiety symptoms. A trial including 11 depressed patients demonstrated a significant reduction in anxiety symptoms (Hamilton Anxiety Rating Scale (HAM-A)) following ketamine infusion (mean HAM-A pretreatment score  $23.4 \pm 6.5$ ; mean HAM-A score after 230 minutes  $14.3 \pm 7.8$ ;  $t(9) = 3.39$ ,  $p < .01$ , Effect Size=1.4)(Salvadore, Cornwell et al. 2009). This improvement is supported by one of the earlier placebo-controlled trials of ketamine which demonstrated that the psychic anxiety item was one of 4 (out of 21) items on the HAM-D demonstrating significant improvement after ketamine infusion (Hofmann, Newman et al. 1995, Zarate, Singh et al. 2006). We propose a randomized, placebo-controlled crossover study to explore the efficacy and time course of action of intravenous ketamine in the treatment of SAD.

3. **Research Plan:** Summarize the study design and research procedures using non-technical language that can be readily understood by someone outside the discipline. Be sure to distinguish between standard of care vs. research procedures when applicable, and include any flowcharts of visits specifying their individual times and lengths. Describe the setting in which the research will take place.

- We propose a crossover trial in which 18 adults with severe SAD will be given a single infusion of ketamine or saline (placebo) and their SAD symptoms will be followed over a two week period.
- We will require at least a 4-week interval between infusions in order to minimize carryover effects.
- An 18 subject crossover trial will give us sufficient power to demonstrate a significant effect of ketamine (compared to placebo) if the symptom improvement is comparable to that observed in Major Depressive Disorder.

**Overview:**

We propose a double-blind, placebo-controlled crossover trial to study the effects of intravenous ketamine for the treatment of SAD. All patients will be offered the option of at least one first line treatment (an SSRI, SNRI, or CBT) prior to study enrollment.

We will perform the first blinded infusion (ketamine or saline) on the first study day. The second blinded infusion (ketamine or saline) will be administered 28 days after the initial infusion. The study investigators will be blinded to the order of infusion which will be determined offsite by the Connecticut Mental Health Center (CMHC) Investigational Drug Service. The infusions will occur on the Clinical Neuroscience Research Unit (CNRU). Patients will be followed with clinical ratings and behavioral assessments for 2 weeks following each infusion. Clinical ratings (excluding the infusion day) will take place at a separate location (the Yale Child Study Center) by a rater unaware of clinical and side-effect ratings on the day of infusion. The side-effects and psychotomimetic ratings for ketamine will be performed by a separate rater, than the ratings of anxiety and depression. We chose this design because the psychometric and physiologic side-effects of ketamine often lead to unblinding and because the beneficial effects of ketamine have lasted for 3 weeks in depression, making the carry-over effects in shorter-duration crossover studies problematic.

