and severity of the adverse events and determine if modifications to the protocol or consent form are required.

- d. For multi-site studies for which the Yale PI serves as the lead investigator: N/A
  - i. How will adverse events and unanticipated problems involving risks to subjects or others be reported, reviewed and managed?
  - ii. What provisions are in place for management of interim results?
  - iii. What will the multi-site process be for protocol modifications?

**12. Statistical Considerations:** Describe the statistical analyses that support the study design.

We will use a paired t-test to compare average improvement over the first 3 days following infusion between ketamine and saline. Ketamine greatly reduces anxiety and depressive symptoms in MDD with an effect size of 1.4-1.5 in similarly designed saline controlled studies (Zarate, Singh et al. 2006). If ketamine proves to be as efficacious in SAD as it is in MDD, a sample size of 18 would allow a placebo to ketamine comparison study to have statistical power greater than 0.80 to detect a statistically significant change at the  $\alpha = 0.05$  level (Cohen 1988). However, it is quite possible that the benefits of ketamine will be smaller in SAD than depression. Therefore, even if the results of our primary analysis are not statistically significant, we would consider having 6 of 18 patients exhibiting a response to ketamine (but not placebo) during the first week following infusion as sufficient evidence towards conducting a more definitive trial. Treatment response is defined as at least a 30% reduction in VAS scores anytime in the first 3 days following infusion.

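### Carry-over is handled by washout alone: the primary test names no baseline for improvement and makes no use of the pre-infusion VAS taken on Day 28

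*Combined protocol and SAP*

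**What the plan says.** All references are to the combined protocol and SAP.

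- **Washout.** Section V, item 1: "We will require 4 weeks between infusion doses in order to minimize carryover effects". Item 3 (Overview) gives the background: "the beneficial effects of ketamine have lasted for 3 weeks in depression", which is why the authors rejected shorter crossovers. The text after Table 1 fixes the gap at 28 days.
- **Endpoint.** Item 1: "Our primary outcome will be average improvement during the first 3 days following infusion on the Visual Analog Scale (VAS) of Anxiety States". No reference value is named.
- **Primary analysis.** Item 12: "We will use a paired t-test to compare average improvement over the first 3 days following infusion between ketamine and saline". There is no period or sequence term, no look at carry-over and no sensitivity analysis.
- **Fallback.** If the primary result is not significant, 6 of 18 patients responding to ketamine but not to placebo would justify a larger trial. Response is a VAS fall of at least 30% at any time in the first 3 days, again with no baseline named.
- **Data already scheduled.** Table 1 has one block of columns for both infusion days and marks the VAS at -1 hour. Its footnote says the VAS is taken both before and after the impromptu speech. Item 10 lists symptom ratings only to day 14 after each infusion; the day 21 and day 28 contacts are for safety.

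**The concern.** The paired t-test estimates the ketamine effect without bias only if nothing of the first infusion remains in period 2. The plan relies on the washout for this. The margin beyond the quoted duration is one week, it comes from depression rather than social anxiety disorder, and the trial does not plan to examine it.

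The missing baseline makes this matter more. If improvement is taken from Day 0 or screening, benefit that persists in a ketamine-first patient is credited to saline. If it is taken from the same period's pre-infusion rating, most of that benefit is subtracted. Item 12 allows either reading, for the primary endpoint and for the response rule, so the choice could be made after the data are seen. The Day 28 pre-infusion VAS is the only scheduled symptom rating between day 14 and the second infusion. It is therefore the only direct evidence of return to baseline, and the plan gives it no use.

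**Working it through.** **Inputs from the documents.** n = 18; effect size 1.4-1.5; alpha 0.05; stated power above 0.80 (all item 12); gap 28 days; quoted duration 3 weeks = 21 days, so the margin is 28 - 21 = 7 days.

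**Assumptions, none given in the documents.** Two-sided alpha, nine patients per order, no dropout, additive carry-over, and every residual fraction below.

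**1. The plan's own figure.** By the noncentral t, a paired test with n = 18 has power 0.9999 at a standardised paired difference of 1.4, and more at 1.5. The stated figure is met. The smallest paired effect with 80% power is 0.70.

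**2. Common baseline.** Let D be the true effect and c the fraction still present on days 1-3 of period 2. A common baseline cancels from each patient's ketamine-saline difference. The expected difference is D(1 - c) in ketamine-first patients and D in saline-first patients, so the mean is

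[D(1 - c) + D] / 2 = D(1 - c/2).

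The loss is 5% at c = 10%, 12.5% at 25% and 25% at 50%. The variance also rises by (cD)²/4.

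| c | power at 1.4 | power at 0.70 |
|---|---|---|
| 0 | 0.9999 | 0.80 |
| 10% | >0.999 | 0.758 |
| 25% | 0.998 | 0.685 |
| 50% | 0.977 | 0.544 |

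**3. Baseline choice under gradual decay.** Take exponential decay from day 2, with a fraction g left at day 21. Let b be the fraction left at Day 28 and p the mean fraction left on days 29-31. The bias as a share of D is -p/2 with a common baseline and (b - p)/2 with change from each period's own baseline.

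| g at day 21 | b | p | common baseline | own-period baseline |
|---|---|---|---|---|
| 5% | 1.7% | 1.2% | -0.6% | +0.2% |
| 10% | 4.3% | 3.4% | -1.7% | +0.5% |
| 25% | 15.0% | 13.0% | -6.5% | +1.0% |
| 50% | 38.7% | 36.0% | -18.0% | +1.4% |

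If the period baseline enters as a covariate with slope k between 0 and 1, the bias is (k × b - p)/2, which lies between the two columns.

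**4. Noise cost of a raw change score.** Let s² be the variance of one VAS rating. If all ratings within a patient correlate equally at r, the ketamine-saline difference in 3-day means has variance 2s²(1 - r)/3 with a common baseline. Own-period change scores add 2s²(1 - r), giving 8s²(1 - r)/3, which is four times as large. If ratings within a period correlate at w and ratings across periods at v, the two variances are 2s²[(1 + 2w)/3 - v] and 8s²(1 - w)/3. The change score is then less noisy once w exceeds (1 + v)/2.

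**5. Precision of the checks, 9 versus 9.**
- Day 28 shift by order: the 95% CI half-width is 2.12 × √(2/9) = 1.0 SD. Power is 17% for a 0.5 SD difference and 51% for 1 SD.
- Period-1-only comparison: power is 0.796 at 1.4, 0.848 at 1.5 and 0.29 at 0.7, in between-patient SDs. Item 12 does not say how its effect size is standardised. The 1.4 in the Background is a before-after change: (23.4 - 14.3)/6.5 = 1.4.

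**6. Response rule.** With a Day 0 baseline, a ketamine-first patient whose VAS is still 30% below Day 0 at the second infusion counts as a saline responder without any further change, and so drops out of the 6-of-18 count.

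**The case against.** The strongest reply is that the plan dealt with carry-over by design. It calls carry-over a problem for shorter crossovers and chose a gap longer than the only duration it quotes. That stands. A reader might infer that the protocol contradicts itself, or admits a carry-over problem and then ignores it. The text supports neither: this is an untested assumption, not a contradiction.

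A reader might also infer a bias of equal size in either direction, plus or minus c/2. The upward limit requires a sizeable benefit to survive 28 days and then vanish before the day 1-3 ratings. Gradual decay gives at most +1.4% in the range examined. The realistic risk is one-sided, against ketamine, and arises with a common baseline. Nothing in the documents supports a residual as large as 25-50%.

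Three further points hold in part.
- An own-period change score can add noise (step 4), so the baseline is better used as a covariate than by plain subtraction.
- The checks are imprecise. The pre-infusion VAS could also differ by order through anticipation, since item 9 says some people find ketamine's effects frightening.
- Ratings to day 14 and the stated interest in time course give some indirect evidence. If benefit has gone by day 14, carry-over at Day 28 is unlikely. These ratings do not cover the case where it has not.

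The study is a small pilot, which argues for a modest remedy. But its fallback rule decides whether a larger trial follows, and that rule shares the undefined baseline.

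**Conclusion.** The point holds as a gap in the analysis specification that should be closed before unblinding. The baseline for the primary endpoint and for the 30% response is undefined, and that choice decides whether residual benefit matters. With a common baseline the contrast shrinks by c/2; under the decay patterns examined this is 0.6% to 18%. With own-period change the bias is about +0.2% to +1.4%.

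A reader might conclude that the sample-size statement fails. It does not: at an effect of 1.4, power stays at 0.977 even with half the benefit carried over. What is exposed is the estimate, the 6-of-18 count, and power at the smaller effects that item 12 itself considers quite possible (0.80 falling to 0.685 at a paired effect of 0.70 and c = 25%).

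These sizes rest on the assumptions listed in the working. The missing baseline and the unused Day 28 rating do not.

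**What to change.** Amend item 12 as follows.

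1. Define improvement and the 30% response against the same period's -1 hour, pre-speech VAS-Anxiety. Analyse each patient's ketamine-minus-saline difference in the day 1-3 mean, with the difference in period baselines as a covariate and a period term (infusion order coded +1/-1). Read the treatment effect at a baseline difference of zero.
2. Report Day 28 minus Day 0 pre-infusion VAS by infusion order, with a 95% CI, as description only.
3. Report the period-1-only ketamine-versus-saline comparison as a sensitivity analysis whatever item 2 shows. It must not be a switch triggered by a carry-over test.

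**Cost.** No new visits or patients: some SAP wording, two short tables, and two degrees of freedom in the primary model (17 become 15). The checks can expose gross carry-over. With a half-width of about 1.0 SD on the Day 28 shift and period-1 power of 0.29 at 0.7 SD, they cannot exclude a modest amount, and the report should say so.
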